10.3.7 Specimen Collection Summary (8/13/15)

Specimens for Central Review (mandatory for patients with oropharyngeal cancer) and Tissue Banking (highly recommended)			
Specimens taken from patient:	Collected when:	Submitted as:	Shipped:
Representative H&E stained slides of the primary tumor	Pre-treatment	H&E stained slide Pre-treatment	Slide shipped ambient
A corresponding paraffin-embedded tissue block of the primary tumor taken before initiation of treatment or three 2 mm diameter cores of tissue, punched from the tissue block with a punch tool and embedded in paraffin with 4 unstained slides	Pre-treatment	Paraffin-embedded tissue block or block with 3 punch biopsies with 4 unstained slides Note: If site is not allowed to send blocks or punches, then 15 unstained slides will be allowed, but this is an exception.	Block or punch block shipped ambient; include a cold pack during warm weather.

Specimens for Banking and Translational Research (highly recommended)			
Specimens taken from patient:	Collected when:	Submitted as:	Shipped:
PLASMA: 5-10 mL of anticoagulated whole blood in EDTA tube #1 (purple/lavender top) and centrifuge	Pre-treatment, end of radiation therapy (or within 2 weeks of end of radiation therapy), and at 6 mos. from the end of treatment.	Frozen plasma samples containing 0.5 mL per aliquot in 1 mL cryovials (five to eight)	Plasma sent frozen on dry ice via overnight carrier
DNA: 5-10 mL of anticoagulated whole blood in EDTA tube #2 (purple/lavender top) and mix	Pre-treatment (If site missed this collection they can collect this specimen at any time point or at follow up but this must be noted on the ST)	Frozen whole blood samples containing 1 ml per aliquot in 1ml cryovials (three to five)	Whole blood sent frozen on dry ice via overnight carrier

10.3.8 (8/13/15) Submit materials for Tissue Banking, Central Review, Translational Research as follows:

U. S. Postal Service Mailing Address: For Non-urgent, Non-frozen Specimens Only
Biospecimen Bank at UCSF
University of California San Francisco
[name]
[name]
[name]

Courier Address (FedEx, UPS): For Frozen Specimens and Urgent FFPE Samples
Biospecimen Bank at UCSF
[name]
[name]

10.4 Reimbursement

The RTOG Foundation will reimburse institutions for submission of protocol-specified biospecimen materials sent to the Biospecimen Bank at UCSF. After confirmation from the Biospecimen Bank that appropriate materials have been received, ACR Clinical Trials Administration will authorize payment according to the schedule detailed in the study-specific contract.

10.5 Confidentiality/Storage

(See the RTOG Patient Tissue Consent Frequently Asked Questions, <http://www.rtog.org/Researchers/BiospecimenResource/BiospecimenResourceFAQs.aspx> for further details.)

- 10.5.1** Upon receipt, the specimen is labeled with the RTOG protocol number and the patient's case number only. The Biospecimen Bank at UCSF database only includes the following information: the number of specimens received, the date the specimens were received, documentation of material sent to a qualified investigator, type of material sent, and the date the specimens were sent to the investigator. No clinical information is kept in the database.
- 10.5.2** Specimens for tissue banking will be stored for an indefinite period of time. Specimens for central review will be retained until the study is terminated. Specimens for the translational research component of this protocol will be retained until the study is terminated, unless the patient has consented to storage for future studies. If at any time the patient withdraws consent to store and use specimens, the material will be returned to the institution that submitted it.

11.0 PATIENT ASSESSMENTS

11.1 Study Parameters: See Appendix I for a summary of assessments. See Section 11.2 below for details of assessments and exceptions.

11.2 Details of Assessments (8/13/15)

- 11.2.1** It is necessary to repeat the ECHO or MUGA at week 12 (4 weeks post-completion of radiation therapy); see Section 7.7.2.
- 11.2.2** A chest CT scan, or a PET/CT scan must be done within 42 calendar days prior to registration to rule out metastatic disease. In addition, a contrast enhanced CT scan or MRI or PET/CT scan of the tumor site and neck nodes must be done within 42 calendar days prior to registration. Note: The CT scan of the neck and/or PET/CT performed for radiation planning may serve as both staging and planning tools.
- 11.2.3** If the patient consents to submission of tissue and blood for translational research, primary tumor tissue will be submitted pre-treatment, and peripheral blood will be submitted pre-treatment, at the end of radiation therapy, and at 6 months from end of treatment.
- 11.2.4** Patients will be asked to document daily lapatinib/placebo on a pill diary during concurrent treatment and maintenance treatment, which will be collected by the institution as source documentation. Institutions will submit the **DP** form to RTOG at the end of concurrent treatment and every month during maintenance treatment (see Section 12.1).
- 11.2.5** Evaluation During Radiotherapy
- A brief history and physical by a Radiation Oncologist and/or Medical Oncologist must be done weekly.
 - Bilirubin and AST/ALT must be done 4 weeks after start of lapatinib/placebo.
- 11.2.6** Evaluation in Follow Up
- Patients will be seen in long-term follow up every 3 months for years 1 and 2, every 6 months for years 3-5 and then annually until publication of study results.
 - A brief history and physical by a Radiation Oncologist and/or Medical Oncologist and/or ENT or Head & Neck Surgeon must be done at 4 weeks and 3 months from the end of radiation treatment, then every 3 months through year 2, every 6 months for years 3-5, then annually. A laryngopharyngoscopy (mirror and/or fiberoptic and/or direct procedure) is recommended at these time points but is not required.
 - Post-radiation imaging evaluation of the primary tumor and neck at 3 months from the end of radiotherapy is required. The post-radiation imaging can be contrast enhanced CT, MRI, or PET/CT of the head and neck or "whole body" PET/CT (minimum neck and chest),

based on the preference of the treating clinician. However, if a pre-treatment PET/CT was performed, it is highly recommended that a post-radiation PET/CT be used as the post-radiation imaging modality.

Post-radiation imaging evaluation (CT scan or MRI) of the primary tumor and neck also must be done at 6 and 12 months from end of treatment, then annually until year 5.

- A chest CT scan must be done at 6 and 12 months from end of treatment, then annually until year 5.

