7.2.2 Lapatinib/Placebo: (1/16/14)

Note: See Section 7.2.2.1 for lapatinib/placebo feeding tube administration. See Section 7.6.2 for lapatinib/placebo dose modifications.

Week 1: Starting 7 calendar days prior to radiation, patients will take 6 lapatinib/placebo tablets (1500 mg) once daily, 7 days a week, by mouth or by feeding tube on an empty stomach (either 1 hour before or 1 hour after meals). Lapatinib/placebo tablets are **not** to be crushed.

Weeks 2-7: Concurrent with radiation and cisplatin, patients will take 6 lapatinib/placebo tablets (1500 mg) once daily, 7 days a week, by mouth or by feeding tube on an empty stomach (either 1 hour before or 1 hour after meals). Lapatinib/placebo tablets are **not** to be crushed.

After Concurrent Treatment (Maintenance): After completion of radiation, patients will continue lapatinib/placebo 6 tablets (1500 mg) once daily, 7 days a week, by mouth or by feeding tube on an empty stomach (either 1 hour before or 1 hour after meals) for 3 months.

Patient Diary: Patients will be asked to document daily lapatinib/placebo on a pill diary during concurrent treatment and maintenance, which will be collected by the institution as source documentation. Institutions will submit the DP form to RTOG at the end of concurrent treatment and every month during maintenance treatment (see Sections 11.2.3 and 12.1).

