7.4.6 Lapatinib Adverse Events

7.4.6.1 Cardiac: Cardiovascular events have been seen in patients taking other compounds that inhibit ErbB2 when used in combination with or following anthracyclines, and interstitial pneumonitis has been reported in patients taking compounds that inhibit ErbB1. See Sections 7.7.1 and 7.7.2 for management guidelines.

7.4.6.2 Hepatotoxicity: Hepatobiliary events have been seen in patients taking lapatinib and other tyrosine kinase inhibitors. See Section 7.7.3 for management guidelines.

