Cardiac* *Severity corresponding to NYHA criteria; see Appendix II.	Lapatinib therapy to be discontinued permanently in the case of symptomatic NYHA class III and IV congestive heart failure OR decrease in LVEF by $> 20\%$ relative to baseline or less than the institution's lower limit of normal.

Abnormal Liver Function Tests	
In the event of grade 3 or 4 abnormal ALT and/or bilirubin, lapatinib must be discontinued permanently. Refer to Section 7.7.4.
 
For grade 1 or 2 abnormal ALT/bilirubin, lapatinib must be discontinued permanently for patients with:
 
 • BOTH bilirubin and ALT abnormalities being of grade 2 
OR
 
 • EITHER bilirubin OR ALT abnormality is grade 2 and accompanied by signs or symptoms which, in the opinion of the treating physician, are related to liver injury caused by lapatinib. 
Such signs and symptoms may include abdominal pain, fever, jaundice, rash, eosinophilia or a PS drop of ≥ 1 point from baseline. Refer to Section 7.7.4.

In case of multiple short interruptions of dose due to either adverse events or drug supply or other reasons the sum of days without lapatinib treatment should not exceed 21 days in any 90 day treatment period.
	

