7.7.4.1 Permanent Discontinuation Criteria

If a patient experiences ALT $> 3 \times$ ULN and total bilirubin $> 2.0 \times$ ULN ($> 35\%$ direct; bilirubin fractionation required), then the following actions must be taken:

- Immediately and permanently discontinue investigational product;
- In addition to the liver event follow up assessments, the following are suggested: specialist or hepatology consultation; anti-nuclear antibody, anti-smooth muscle antibody, and Type 1 anti-liver kidney microsomal antibodies; and liver imaging and/or liver biopsy to evaluate liver disease;
- Promptly report the event to Novartis within 24 hours of learning its occurrence;

- Monitor every 7 calendar days until liver chemistries resolve, stabilize or return to within baseline values;
- Do not re-challenge with investigational product.

NOTE: If bilirubin fractionation testing is unavailable and a patient meets the criterion of total bilirubin $>2.0 \times \text{ULN}$, then the management of hepatotoxicity actions above must still be performed.

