7.7.4.2 Interruption Criteria

If a patient experiences:

- ALT $>8 \times \text{ULN}$ or
- ALT $>5 \times \text{ULN}$ persisting for > 14 calendar days: retest within 3 days from the first occurrence and then every 7 calendar days to determine if ALT elevation persists or
- ALT $>3 \times \text{ULN}$ with signs or symptoms of hepatitis or hypersensitivity (the appearance or worsening of fatigue, nausea, vomiting, right upper quadrant pain or tenderness, fever, rash, or eosinophilia)

then hold investigational product for 14 calendar days, repeat liver chemistry testing in 14 calendar days, and then contact the Principal Investigator, [name], to discuss the possibility of re-starting lapatinib. Liver chemistries and aforementioned signs and symptoms should be monitored at a minimum of every 14 calendar days until resolution, stabilization, or a return to baseline values, at which point monitoring should be continued per protocol.

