Assessments	Prior to Registration (calendar days)	Prior to Treatment (calendar days)	q7 days During Treatment	From End of Radiation Therapy (calendar days)					q 3 mos. in year 2; 6 mos. in years 3-5; then annually*
				4 weeks	3 mos.	6 mos.	9 mos.	12 mos.	
Complete history/physical	28 days		Brief H&P	X*	X*	X*	X*	X*	X*
Rad Oncology Exam				X*	X*	X*	X*	X*	
Med Oncology Exam	28 days			X*	X*	X*	X*	X*	
Zubrod	14 days		X		X	X	X	X	X
Weight	28 days		X		X	X	X	X	X
Chest CT or PET/CT	42 days					X*		X*	Annually until year 5
Contrast enhanced CT or MRI or PET/CT of tumor site and neck nodes	42 days				X*	X*		X*	Annually until year 5
EKG	84 days								
ECHO or MUGA	84 days			X*					
ENT or H&N Surgeon exam	42 days			See Sec. 11.2.5	See Section 11.2.6				
CBC, Diff, Platelets	14 days		X		X	X	X	X	
Na, K, glucose, Ca, Mg	14 days								
Na, K, Cl, glucose, Ca, Mg, albumin			X	X	X	X	X	X	
Bilirubin, AST/ALT	14 days		See Sec. 11.2.5		X	X	X	X	
Serum creatinine or creatinine clearance	14 days		X		X	X	X	X	
Serum pregnancy test, for women of childbearing potential	14 days								
Adverse Event Eval, including mucosal assessment			X	X	X	X	X	X	X
Dental assessment		Recommended at 84 days							
Whole body PET scan		Recommended at 42 days							
Audiogram		Recommended at 84 days							
Swallowing assessment		Recommended at 28 days							
Nutritional eval for PEG tube		Recommended prior to tx							
*Pill Diary			End of tx	q30 days. for 3 mos.					
QOL/PRO assessments, if patient consents		X			X			X	at 24 mos. from end of tx
Tissue/blood for research, if patient consents		Prior to treatment		End of RT		X			

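### One liver test is scheduled on drug, at about day 29, and the next falls as maintenance ends at about day 140, so about 111 of 140 dosing days have no scheduled test that could first reveal a silent ALT or bilirubin rise in time to act

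*Combined protocol and SAP*

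**What the plan says.** **Dosing.** Under section 7.2.2, lapatinib/placebo starts 7 days before RT and continues through RT. Then "After completion of radiation, patients will continue lapatinib/placebo 6 tablets (1500 mg) once daily", for 3 months. Section 6.1 sets RT at 42 calendar days.

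**Liver testing on drug.** Section 11.2.5 has one requirement: "Bilirubin and AST/ALT must be done 4 weeks after start of lapatinib/placebo". In Appendix I the row "Bilirubin, AST/ALT" has a pre-registration test within 14 days and a pointer to 11.2.5 during treatment. It has no mark at 4 weeks after RT, then marks at 3, 6, 9 and 12 months. The row "Na, K, Cl, glucose, Ca, Mg, albumin" is marked every 7 days during treatment and again at 4 weeks after RT.

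**Rules that act on liver values.**
- Section 7.4.6.2 gives the reason for concern: "Hepatobiliary events have been seen in patients taking lapatinib and other tyrosine kinase inhibitors".
- Section 7.6.2: "In the event of grade 3 or 4 abnormal ALT and/or bilirubin, lapatinib must be discontinued permanently". Grade 2 in both ALT and bilirubin also requires a permanent stop.
- Section 7.7.4.1, for ALT above 3 x ULN with total bilirubin above 2 x ULN: "Immediately and permanently discontinue investigational product". Section 7.9.2.1 makes the same combination a reportable SAE.
- Section 7.7.4.2 requires a 14-day hold for ALT above 8 x ULN, for ALT above 5 x ULN lasting more than 14 days, or for ALT above 3 x ULN with symptoms. For a persisting rise it sets its own follow-up: "retest within 3 days from the first occurrence and then every 7 calendar days".

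**The concern.** The stop and hold rules need a measured ALT or bilirubin value, and several of them require no symptom. Section 7.7.4 sets close retesting, but only after a first abnormal value is known. First detection is left to the routine schedule, which has one test about a fifth of the way through dosing and the next when dosing is over. A patient whose first silent rise comes after week 4 can stay on 1500 mg daily to the end of maintenance unless someone orders an unscheduled test.

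Symptoms are a weak substitute. Section 7.7.4.2 lists fatigue, nausea and vomiting among the warning signs, but section 6.9 expects fatigue from RT and section 7.3.5 expects nausea and vomiting from cisplatin. Cardiac risk is handled differently: sections 7.7.2 and 11.2.1 require a repeat ECHO or MUGA during maintenance, 4 weeks after RT. The liver has no equivalent check.

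**Working it through.** The plan states no figure for this gap, so the check is calendar arithmetic on its own schedule. Day 1 is the first dose.

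**Inputs**
- Lead-in of 7 days (7.2.2), so RT starts on day 8.
- RT of 42 days (6.1), so RT ends on day 7 + 42 = 49.
- Maintenance of 3 months (7.2.2), taken as 91 days, so the last dose is on day 49 + 91 = 140. The supply agrees: 6 bottles (7.4.8.2) x 90 tablets (7.4.3) / 6 tablets a day = 90 days.
- On-drug liver test 4 weeks after the start (11.2.5): day 1 + 28 = 29.
- Next liver test 3 months after RT (Appendix I): day 49 + 91 = 140.

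**Gap as planned**

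| Case | RT (days) | Maintenance (days) | Last dose | Gap | Share of dosing |
|---|---|---|---|---|---|
| Low (assumed) | 40 | 84 | 131 | 131 - 29 = 102 | 77.9% |
| On schedule | 42 | 91 | 140 | 140 - 29 = 111 | 79.3% |
| High | 50 | 92 | 149 | 149 - 29 = 120 | 80.5% |

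Fifty days is the upper limit of acceptable variation in RT time in section 6.7.

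**Effect of adding tests**
- *End of RT (day 49) and 4 weeks after RT (day 77).* Intervals are 49 - 29 = 20, 77 - 49 = 28 and 140 - 77 = 63 days. The longest is 63 (56 in the low case, 64 in the high case). That leaves 63 of 91 maintenance days (69%) after the last test that can be acted on.
- *If the weekly draws run from day 29* (36, 43, 50), the last one inside RT is day 43. Intervals are 14, 34 and 63, with the same longest interval.
- *Weekly panels during treatment plus 4 weeks after RT.* Seven weekly draws less the one at day 29, plus one, is 7 extra panels; counting the 6 RT weeks only, it is 6. The longest interval is still 63.
- *One more draw at 8 to 9 weeks after RT.* Day 105 splits the 63 days into 28 and 35, day 109 into 32 and 31, and day 112 into 35 and 28. The longest is 32 to 35.

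**Patients who could still benefit**

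Section 13.5 gives accrual of 2.5 a month. The number on drug at any time is 2.5 x 140 / 30.44 = 11.5 (10.8 to 12.2 over the range above). If the arms are equal, about 5.7 of them are on lapatinib. Once accrual has closed, the number still on drug t days later is 2.5 x (140 - t) / 30.44:

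| t (days, assumed) | On drug | On lapatinib |
|---|---|---|
| 30 | 9.0 | 4.5 |
| 60 | 6.6 | 3.3 |
| 90 | 4.1 | 2.1 |

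These counts assume that nobody stops drug early, so they are upper figures. Section 13.6.3 expects concurrent therapy to finish around July 2017. Adding 3 months of maintenance gives about October 2017 for the last dose.

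**The case against.** The strongest objection is that no harm is shown. The documents do not say how often liver rises on lapatinib are silent, when they begin, or what test interval is adequate. The Investigator Brochure cited in section 7.4 is not available here. The share of dosing days without a test describes the calendar and does not measure risk. This stands, and it is why no count of affected patients is given.

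There are also other safeguards: entry limits on bilirubin and AST/ALT (3.1.7), exclusion of active hepatic or biliary disease (3.2.11), weekly examination during RT and another at 4 weeks after it (11.2), adverse event review at those times, and twice-yearly committee review of morbidity (13.6.1). They narrow the exposed group to patients who are normal at week 4, have no symptoms and are not tested at a clinician's discretion. None of them schedules a test for a silent rise.

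Little benefit remains at this date. The latest section date is 3/22/17, and section 13.5 expected accrual to end around March 2017. This also stands and limits the gain, though the cost is correspondingly small.

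Finally, the blank cell is read by column position from an extracted table whose placement is not perfect elsewhere. The electrolyte and albumin row does carry its mark in the 4-week column, which supports the reading, and no misplacement in the liver row has been shown. Section 11.2.1 also equates 4 weeks after RT with week 12, whereas day 77 closes week 11. A draw in week 12 (days 78 to 84) would leave 140 - 78 = 62 to 140 - 84 = 56 days, which changes nothing of substance.

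**Conclusion.** The concern holds. For a patient on schedule, about 111 of 140 dosing days (79%; range 102 to 120 days, 78% to 81%) pass with no scheduled test that could first show a silent ALT or bilirubin rise while dosing can still be changed. This rests on reading the liver row as blank at 4 weeks after RT and on a 3-month maintenance period of about 91 days. It concerns first detection only, since a patient already found abnormal comes under the retesting in section 7.7.4. The 3-month test may fall a few days before the last dose, but almost no dosing is then left to stop.

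The schedule should be corrected because mandatory stop rules need a scheduled measurement and the correction is cheap. The number who would benefit is small: at most about 9 to 4 patients on drug (about 4.5 to 2 on lapatinib) if the change takes effect 30 to 90 days after accrual closes.

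**What to change.** Amend section 11.2.5 and the liver row of Appendix I so that bilirubin and AST/ALT are added to chemistry blood already drawn, at minimum at the last weekly draw of RT (about day 43 to 49, depending on the draw days) and at 4 weeks after RT (about day 77). Weekly panels during treatment are an alternative, but they do not shorten the longest interval further.

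This narrows the gap without closing it, since about 63 days of maintenance would still have no scheduled test. The sponsor's clinicians should decide whether to add one test at 8 to 9 weeks after RT. Sections 8.1 and 8.2 imply a clinical assessment at that time, but Appendix I has no visit there, so it would need an extra draw. The thresholds and actions in 7.6.2 and 7.7.4 stay as they are, and the endpoints, blinding and analysis are unaffected.

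The cost is a short amendment with site IRB processing and two liver panels per patient on existing samples, with no new visit. The weekly option costs 6 to 7 extra panels, and the optional later test costs one draw. The downside is minor laboratory expense and a few incidental abnormalities to follow up. With the last courses due to end about October 2017, the change is useful only if made promptly.

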11.3 Measurement of Response/Progression

11.3.1 Response versus “Tumor Clearance” versus Cancer Progression

Response and confirmation of local (primary site) or regional (neck) “tumor clearance” are not endpoints in this study. Clinical or radiographic evidence of progressive local-regional disease beyond 20 weeks should be documented in the clinical record and ideally confirmed by local or regional biopsy, neck dissection, or salvage surgery. CT or MRI (of head and neck region, with Chest CT), or PET/CT (including chest anatomy) may be used as radiographic evaluation of overall cancer status. The primary, neck and chest portions of the scans should be evaluated and reported separately. The CT portion of a PET/CT may serve as sufficient radiographic evaluation of the chest. If CT or MRI is used for evaluation of the head and neck region, CT of chest will be needed to rule out distant disease or second primaries at the designated evaluation intervals as outlined above in Section 11.2.6 and Appendix I.

11.3.2 Local or Regional Progression

Local (primary site) or regional (neck) progression is defined as palpable residual disease or CT/MRI evidence of persistent disease at the primary site or neck. The location of progressive disease should be separately distinguished (local vs. neck) to document the precise pattern of failure if possible. Progression of local or regional disease should be confirmed by biopsy when possible but may be clinically assessed and documented in the clinical record at the judgment of the treating clinicians.

